3.3 Outcome measures/endpoints

Outcome measures were determined after discussions with PPIE collaborators and a search of the COMET Initiative database (terms "Neurology", "Acute Stroke", "Published") for acute stroke trial core outcome sets. Two published recommendations were identified [29, 30] which incorporate survival, stroke recurrence, patient reported outcome measures (PROMs) across all domains including motor/non-motor problems, cognition, mood. However, whilst mRS is a standard outcome measure, there is no ubiquitous or agreed set of outcome/assessment scales used consistently in acute stroke trials. Outcome measures were chosen in partnership with the CLASP PPIE group and are aligned with the above recommendations to include survival, stroke recurrence and PROMs (quality of life and stroke-related health status). Caregiver burden was considered to be an important outcome measure by the PPIE group in view of the relatively poor prognosis of patients with PSP. The primary and secondary outcome measure scales (mRS [31], EQ-5D-5L [32], Home time [33], Stroke Impact Scale [34] and Zarit Caregiver Burden [35]) are well-established in stroke research and can be collected using telephone and postal assessments. The assessments will be centralised and undertaken by research staff blinded to treatment allocation. The timing of outcome assessments (described below) refers to time from randomisation.

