3.3.2 Secondary outcomes

- All-cause mortality at 90 days
- Days spent in pre-admission usual place of residence at 90 days
- Cardiovascular mortality at 90 days
- Non-elective admissions by 90 days
- Stroke at 90 days
- Major cardiovascular events at 90 days
- EQ-5D-5L at 90 days
- Stroke Impact Scale at 90 days
- Zarit Caregiver Burden (ZBI-12) interview
- Clostridioides difficile infection within 90 days
- Ventricular arrhythmia within 7 days
- Health and social care resource use (index hospitalisation and post-discharge health and social care contact) up to 90 days to inform health economic analysis.

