7.6 Follow-up assessments

The trial will comprise of 4 visits: Screening, Randomisation, Day 7 and Day 90 follow-up.

The Day 7 (+3) visit will be carried out by research staff who will collect information such as the following from case notes:

- Information on safety outcomes including *C.difficile* infection, and occurrence of defined SAEs (see section 9)
- Clarithromycin dose, doses administered and route(s) of administration (including reasons for any non-administered doses)
- Other antibiotics and doses received
- Highest CRP concentration (mg/L) to Day 7 (+3) visit
- Highest WBC count and neutrophil count (x10⁹/l) to Day 7 (+3) visit
- Highest RR (/minute) to Day 7 (+3) visit
- Highest temperature (°C) recorded to Day 7 (+3) visit
- Highest NEWS-2 score to Day 7 (+3) visit
- Lowest oxygen saturations (%) to Day 7 (+3) visit
- Oxygen requirements
- Presence of unilateral or bilateral chest signs on examination
- Findings from clinical CXR or other chest radiology
- Contact details for follow-up (participant, consented caregiver, GP)

Participants and their caregivers/GP can be contacted by telephone, email or post between 1 week and 1 month prior to the due date of the Day 90 visit to confirm contact details and ongoing participation.

The Day 90 visit will involve local data collection by the research team and a centralised assessment (+/-7 for local research staff follow-up, +/-14 for central follow-up) by video or telephone.

Local research staff will collect the following data from the medical record at Day 90 (+/-7):

- Length of hospital stay (days)
- Mortality
- Discharge destination (remains in hospital, home, care home)
- Urgent or unplanned re-admissions
- Recurrent stroke or other vascular events

The centralised assessment will then be undertaken by appropriately trained University of Manchester staff blinded to treatment allocation. This will take place via video or telephone assessment after local research staff have carried out the mortality check. They will collect information such as the following measures:

- mRS
- Quality of Life (EQ-5D-5L)
- Stroke Impact Scale (SIS)
- Home time (number of days at usual place of residence [immediately prior to their admission] at day 90)
- Health and social care resource use (index hospitalisation and post-discharge health and social care contact up to 90 days)
- Caregiver quality of life (EQ-5D-5L)
- Zarit Caregiver Burden (ZBI-12)

The Day 90 visit marks the end of the study.

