9.2 Operational definitions for (S)AEs

Clarithromycin has been in clinical use for more than 30 years and is widely used for the treatment of respiratory tract infections, including community acquired infection. The IMP is generally well tolerated with the most common side effects being mild gastrointestinal adverse reactions. It has a well-defined safety profile obtained throughout the lifetime of the drug and therefore it is highly unlikely that this trial will identify any novel (serious) adverse reactions. Participants are anticipated to exhibit complications related to the index stroke, associated complications, and comorbidities resulting in prolongation of hospitalisation and high numbers of adverse events due to the short time frame between the index stroke and the commencement of treatment with IMP. In addition, participants may receive multiple treatments to manage stroke symptoms, and associated underlying medical conditions. Under these circumstances, participants may be subject to multiple ongoing adverse events and serious adverse events and it may be difficult for investigators to distinguish AEs and SAEs that are a consequence of disease processes and concomitant medications from those that have a causative relationship with the IMP(s) due to a high level of confounders. Taking the above into account, (S)AEs (except for those detailed below) will not be reported via the eCRF but must be recorded within participant medical records in accordance with GCP.

The principal risk associated in adding clarithromycin to the usual care pathway is the potential for prolongation of the QT and QTc interval resulting in cardiac arrythmias; primarily ventricular arrythmias. In addition, treatment with antimicrobial therapies, including macrolides, can be associated with an increased risk of developing infection with *C.difficule*. While cardiac arrythmias and *C.diff* infections may not necessarily always meet the regulatory definition of serious, they will almost certainly require intervention to prevent them from become so and are significant medical events.

Therefore, the following events will be subject to expedited reporting as serious adverse events from the point of randomisation until day 3 post cessation of trial IMP (generally, day 7 or earlier but could be up to day 10 after randomisation):

- Any suspected or confirmed infection with *C.difficile* irrespective of whether the event meets the regulatory definition of serious.

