- Any incidence of sustained (>30s) ventricular arrythmias irrespective of whether the event meets the regulatory definition of serious.
- Any serious adverse event suspected to be directly related to the IMP that is considered unexpected by the local investigator.

Note: If an event occurs more than 72 hours after cessation of IMP that is considered related to IMP, it must be reported.

Hospitalisation, or prolongation of hospitalisation, related to the index stroke and associated complications, or other underlying medical conditions are excluded from reporting as a serious adverse event for the purpose of this trial. Such events should be recorded within the eCRF at visit 2 and visit 3 (day 90) as per routine data collection and will be used to inform trial endpoints. The IDMC will review event rates on a regular basis to ensure the frequency of these events is line with expectations.

The following are exempted from recording within the eCRF and reporting as SAEs:

- Routine treatment or monitoring of the studied indication not associated with any deterioration in condition.
- Treatment that is elective or pre-planned, for a pre-existing condition not associated with any deterioration in condition, e.g. pre-planned hip replacement operation which does not lead to further complications.
- Any admission to hospital or other institution for general care where there was no deterioration in condition.
- Treatment on an emergency, outpatient basis for an event not fulfilling any of the definitions of serious as given above and not resulting in hospital admission.

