9.3 Recording and reporting of Adverse Events

All AEs from the time of consent until 2 days post cessation of IMP that are observed by the Investigator or reported by the participant will be recorded in the participant's medical records.

In accordance with section 9.2, any confirmed or suspected *C.difficile* infections or ventricular arrythmia occurring from the point of consent until day 3 post cessation of trial IMP (generally, day 7 or earlier but could be up to day 10 after randomisation) must be reported in accordance with section 9.4.

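### The ventricular arrhythmia outcome and the rules for reporting it differ in event definition, start point and window, and the reporting window has no end date in the usual care arm

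*Protocol*

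**What the plan says.** All references are to the protocol.

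- **Outcome (3.3.2, also the Trial Summary).** The outcome is "Ventricular arrhythmia within 7 days". Section 3.3 sets the clock: "The timing of outcome assessments (described below) refers to time from randomisation". No duration threshold or arrhythmia type is given. In the Trial Summary it is one of two outcomes listed against the objective that the treatment is safe.
- **Section 9.2.** The expedited list contains "Any incidence of sustained (>30s) ventricular arrythmias irrespective of whether the event meets the regulatory definition of serious". The window runs "from the point of randomisation until day 3 post cessation of trial IMP (generally, day 7 or earlier but could be up to day 10", the days being counted from randomisation. Adverse events outside the list, serious or not, are kept out of the eCRF and left to the medical records. Events more than 72 hours after the drug stops are reportable only if considered related to it.
- **Section 9.3.** This section says it follows 9.2, but requires reporting of "any confirmed or suspected *C.difficile* infections or ventricular arrythmia occurring from the point of consent until day 3 post cessation of trial IMP". The threshold is absent and the start is consent, not randomisation. It sends these events to 9.4.
- **Section 9.4.1.** SAEs as defined in 9.2 go into the eCRF, counted from consent.
- **Section 7.6.** At Day 7 (+3), research staff read the case notes for safety outcomes, with *C. difficile* as the named example, "and occurrence of defined SAEs (see section 9"). Ventricular arrhythmia is not named.

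**The concern.** Section 9.2 describes arrhythmia, mainly ventricular, as the main risk of adding clarithromycin, so this outcome carries much of the safety comparison. Two things can go wrong.

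First, the sections do not agree on what counts. A site that sees a 20-second episode finds it inside the outcome as worded in 3.3.2, reportable under 9.3, and not reportable under 9.2 or 9.4.1.

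Second, the reporting window is anchored to stopping a drug that only one arm receives. In the clarithromycin arm it lengthens or shortens with the number of doses taken. In usual care the anchor does not exist. Treatment is open label for participants and care providers (7.4), so a difference in how long or how closely the arms are observed bears directly on the comparison of event counts.

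**Working it through.** **1. The definitions side by side**

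| Section | Event | Start | End |
|---|---|---|---|
| 3.3 and 3.3.2 (outcome) | ventricular arrhythmia, no threshold | randomisation | day 7 |
| 9.2 | sustained, over 30 s | randomisation | drug cessation + 3 days |
| 9.3 | ventricular arrhythmia, no threshold | consent | drug cessation + 3 days |
| 9.4.1 | as defined in 9.2 | consent | drug cessation + 3 days |
| 7.6 (Day 7 notes) | safety outcomes and defined SAEs; arrhythmia not named | not stated | Day 7 (+3) visit |

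No row of the reporting rules matches the outcome row on event, start and end together.

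**2. The protocol's own window figure**

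Section 9.2 gives the end as generally day 7 or earlier and at most day 10. Section 8.6 allows the 10 doses to be spread over at most 7 days, so the latest end is 7 + 3 = day 10, as stated. An uninterrupted course ends slightly later than the general figure: dose 10 falls at (10 − 1) × 0.5 = day 4.5, and 4.5 + 3 = day 7.5. If cessation is counted as the end of day 5, it is 5 + 3 = day 8.

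**3. When the window closes before day 7**

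Inputs: a dose every 12 hours (8.6), 3 days after cessation (9.2), and the first dose at randomisation (assumption). For *n* consecutive doses, window end = (*n* − 1) × 0.5 + 3 days.

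| Doses taken | Last dose (day) | Window ends (day) |
|---|---|---|
| 1 | 0 | 3.0 |
| 5 | 2.0 | 5.0 |
| 8 | 3.5 | 6.5 |
| 9 | 4.0 | 7.0 |
| 10 | 4.5 | 7.5 |

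Reaching day 7 requires (*n* − 1) × 0.5 + 3 ≥ 7, that is *n* ≥ 9. The window therefore covers the 7-day outcome after 9 or 10 doses and closes early after 8 or fewer. A late first dose or missed doses move the end later.

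**4. Who stops early**

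Section 7.9.1 lists QTc prolongation and ventricular tachycardia among the reasons for withdrawing clarithromycin, and follow-up can continue afterwards. The SAE window can thus shorten for participants in whom arrhythmia is of particular interest.

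**5. Usual care**

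Sections 7.3 and 8.12 give this arm no trial drug. There is no cessation date, so cessation + 3 days is undefined.

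**6. Size**

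The protocol gives neither a ventricular arrhythmia rate nor the share of episodes lasting 30 s or less. The number of events that could be missed cannot be computed.

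**The case against.** The strongest reply is that 9.2 governs expedited SAE reporting and does not define the outcome. A stricter threshold for rapid reporting than for an outcome read from notes is legitimate. The Day 7 review in 7.6 is a separate route: it collects safety outcomes, its list is illustrative, it is not restricted by arm, and it is not tied to drug cessation. Ventricular arrhythmia is one of the listed safety outcomes, so the review can reasonably be read as including it. The schedule in Appendix 9 also has safety entries at Day 7 and at local Day 90. The missing threshold in 9.3 may be shorthand, since that sentence defers to 9.2.

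Much of this stands. A reader might infer that the outcome cannot be measured as defined, that defined SAEs are its only source, or that analysts could never repair the gap. The document supports none of these, because 7.6 offers a second route and the events should be in the medical records. Nor does 3.3.2 say that every arrhythmia of whatever duration counts; it leaves the type open.

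The reply does not remove the conflict. The protocol never says that 7.6 is the source for this outcome. That section names *C. difficile* but not arrhythmia, the Appendix 9 rows refer to SAEs, and 9.2 keeps unlisted adverse events out of the eCRF. Reading 9.3 as shorthand settles the threshold but not the different start points or the missing end date in usual care. The 72-hour exception in 9.2 depends on a judgement of relatedness to the trial drug, so it gives usual care no equivalent.

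**Conclusion.** The point holds as an internal inconsistency with an unspecified capture route. The outcome and its reporting rules differ in event threshold, start point and end of window, and the end is undefined in usual care. After a full course the window does cover day 7; the shortfall in the clarithromycin arm is confined to participants who stop after eight or fewer consecutive doses. That figure assumes 12-hourly dosing from randomisation without interruption.

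The consequence is possible arm-dependent ascertainment of one of the two listed clinical safety outcomes in an open-label trial. It is a risk, not a demonstrated loss, and no count of missed events can be put on it. The primary outcome analysis is unaffected. It should be corrected, because the conflict is in the protocol's own rules and restoring unreported episodes later would mean going back to the notes across at least 45 sites.

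**What to change.** Reconcile sections 3.3.2, 7.6, 9.2, 9.3 and 9.4.1:

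- Give the outcome one event definition, chosen by the trial team, and one start point.
- Name a ventricular arrhythmia item on the Day 7 form. Collect it in both arms over a fixed 7 days from randomisation, independent of when the trial drug stops, and record duration or sustained yes/no.
- If expedited SAE reporting keeps its own threshold, state that it is separate from the outcome, and that the 9.2 limit on eCRF reporting does not apply to the outcome item.
- State when the SAE reporting window ends for usual care participants, and align the start points in 9.2, 9.3 and 9.4.1.

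Recording duration or sustained status lets either definition be applied without this review choosing a clinical threshold. The cost is wording and one eCRF field, filled from a case-note review that already takes place.

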9.3 Recording and reporting of Adverse Events

All AEs from the time of consent until 2 days post cessation of IMP that are observed by the Investigator or reported by the participant will be recorded in the participant's medical records.

In accordance with section 9.2, any confirmed or suspected *C.difficile* infections or ventricular arrythmia occurring from the point of consent until day 3 post cessation of trial IMP (generally, day 7 or earlier but could be up to day 10 after randomisation) must be reported in accordance with section 9.4.

9.4 Recording and Reporting of Serious Adverse Events (SAEs)

9.4.1 Initial reports

All SAEs as defined within section 9.2 must be recorded within the study eCRF from the point of informed consent until day 3 post cessation of trial IMP (generally, day 7 or earlier but could be up to day 10 after randomisation).

Protocol defined SAEs must be reported within the eCRF within 24 hours of investigator or study team awareness of the event.

Full details of these SAEs will be recorded in the eCRF. The following information will be collected at a minimum:

- Nature of the event
- Event duration (start and end dates, if applicable)
- Relationship to trial medication in the opinion of the investigator
- If related, whether the reaction would be considered expected or unexpected
- Action taken
- Outcome (if applicable)
- Seriousness criteria

All protocol defined SAEs will be subject to review by the local Principal Investigator, or their medically qualified designee(s), within 7 days of the site becoming aware of the event for fatal or life-threatening SAEs and within 15 days for all other SAEs.

Any change of condition or other follow-up information should be added to the eCRF as soon as it is Serious Adverse Events must be followed up until the event has resolved or a final outcome has been reached.

9.4.2 Review and follow up of SAEs

Where there is a change in causality, a worsening in the severity, increase in seriousness, or worsening in outcome of an event, then the local investigator is expected to re-review the event within the timelines detailed above. Significant changes in diagnosis, and any additions to the narrative that imply the need for further clinical review may also require re-review by all parties.

9.5 Assessment of Serious Adverse Events

All SAEs reported as per section 9.2 must be assessed for severity, causality and expectedness with reference to this protocol and the Reference Safety Information (RSI).

9.5.1 Assessment of seriousness

CLASP

An adverse event will be considered serious if it:

- Results in death
- Is life threatening
- Requires hospitalisation or prolongation of existing hospitalisation
- Results in persistent or significant disability or incapacity
- · Consists of a congenital anomaly or birth defect
- Intervention is required to prevent one of the above

9.5.2 Assessment of severity

This should be assessed and described using the following categories:

- Mild awareness of event but easily tolerated
- Moderate discomfort enough to cause some interference with usual activity.
- Severe inability to carry out usual activity

NB: "Severe" is often used to describe intensity of a specific event, which may be of relatively minor medical significance. "Seriousness" is the regulatory definition supplied above.

9.5.3 Assessment of causality

i.e. Does the event have a "reasonable causal relationship" with trial medication. A binary Yes/No decision will be used for the assessment of causality.

SAEs will be submitted with a provisional assessment of causality by the reporting investigator. Following this initial submission SAEs must be reviewed for causality by the Principal Investigator, or their medically qualified designee(s) as soon as possible and within 5 days of the site becoming aware of the event for fatal or life-threatening SAEs and 10 days for all other SAEs.

9.5.4 Assessment of expectedness

If the SAE is suspected to be related to IMP, an assessment should be made of the expectedness of the reaction, i.e. is the reaction a recognised adverse effect of the medication.

The Chief Investigator and/or the Sponsor PV Manager (or their delegates) are responsible for the assessment of expectedness of all SAEs deemed to be related to the IMP.

The expectedness of an adverse reaction is assessed against the Reference Safety Information (RSI), i.e. the information regarding expected reactions approved by the MHRA.

Expected events are those consistent with the relevant product information documented in the RSI, i.e. a Serious Adverse Reaction.

Unexpected events are those not consistent with the relevant product information documented in the RSI, i.e. a Suspected Unexpected Serious Adverse Reaction.

9.6 Reference Safety Information

The approved RSI for clarithroymycin in place at the time an SAE occurs will be used to assign expectedness of related events. This will be based on the SmPC for clarithromycin 500mg powder for solution for infusion vials (Bowmed Ibisqus Limited).

9.7 Recording and reporting of SAEs where eCRF web portal access is not possible

If recording in the eCRF is not possible, e.g. problems with the web portal, then a paper SAE form should be completed.

The SAE form is downloaded from https://www.glasgowctu.org/Home/00-safety-reporting/, printed, completed and signed. The form should be scanned and emailed to [contact]. If this website is unavailable, a paper copy of the SAE form template is provided in the Investigator Site File.

9.8 Suspected Unexpected Serious Adverse Reactions (SUSARs)

Any SAE assigned as related by the local investigator, and determined to be unexpected by the CI or Sponsor, will be classified as a SUSAR and subject to expedited reporting to the Medicines and Healthcare products Regulatory Agency (MHRA) and the Research Ethics Committee (REC). If the CI disagrees with the PI's causality assessment, both opinions will be provided on the report.

The Sponsor PV Office will inform the MHRA and the REC of a notifiable SUSAR within the required timescales:

- Fatal or life threatening SUSARs: not later than 7 days after the sponsor had information that the case fulfilled the criteria for a fatal or life threatening SUSAR, and any follow up information within a further 8 days.
- All other SUSARs: not later than 15 days after the sponsor had information that the case fulfilled the criteria for a SUSAR.
- The sponsor will report SUSARs to the MHRA via the ICSR reporting system and to REC by email with accompanying CTIMP Safety Report Form.

